8.3.3.3 EXPECTEDNESS

The study sponsor will be responsible for determining whether an adverse event (AE) is expected or unexpected. An AE will be considered unexpected if the nature, severity, or frequency of the event is not consistent with the risk information previously described for the study intervention.

8.3.4 TIME PERIOD AND FREQUENCY FOR EVENT ASSESSMENT AND FOLLOW-UP

The occurrence of an adverse event (AE) or serious adverse event (SAE) may come to the attention of study personnel during study visits and interviews of a study participant presenting for medical care, or upon review by a study monitor.

All AEs including local and systemic reactions not meeting the criteria for SAEs will be captured on the appropriate case report form (CRF). Information to be collected includes event description, time of onset, clinician's assessment of severity, relationship to study product (assessed only by those with the training and authority to make a diagnosis), and time of resolution/stabilization of the event. All AEs occurring while on study must be documented appropriately regardless of relationship. All AEs will be followed to adequate resolution.

Any medical condition that is present at the time that the participant is screened will be considered as baseline and not reported as an AE. However, if the study participant's condition deteriorates at any time during the study, it will be recorded as an AE.

Changes in the severity of an AE will be documented to allow an assessment of the duration of the event at each level of severity to be performed. AEs characterized as intermittent require documentation of onset and duration of each episode.

The study sponsor will record all reportable events with start dates occurring any time after informed consent is obtained until 7 (for non-serious AEs) or 30 days (for SAEs) after the last day of study participation. At each study visit, the investigator will inquire about the occurrence of AE/SAEs since the last visit. Events will be followed for outcome information until resolution or stabilization.

All participants in the study will have notation on their UNC EPIC chart to alert the research staff if the patient is seen for any possible adverse event. Patients will be assessed for adverse events at their telephone follow up 30 days after study intervention. Solicited information on adverse events will include increased bleeding requiring hospital admission or blood transfusion and infection requiring hospital admission or IV antibiotics. All other adverse events will be identified based on unsolicited questioning during this telephone visit.

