8.3.5 ADVERSE EVENT REPORTING

Adverse event reporting by patient self-report will take place at each study visit, both in person and via telephone. Additionally, any adverse event that happens between study visits for which the participant seeks care at UNC Chapel Hill will be abstracted from the UNC EPIC electronic medical record. All adverse events will be recorded on case report forms (CRF) and will be reviewed by the principal investigator and mentor. Case report forms should be documented within 24 hours of the event, and review of the case report forms will occur on a weekly basis.

Likely mild medication side effects as detailed for UPA include headache (18%), nausea (12%), abdominal pain (12%). Other infrequent mild side effects include dysmenorrhea, fatigue and dizziness [14]. All patients may experience pain and discomfort during the process of pregnancy expulsion; however, this pain and discomfort are not different than what a patient would experience not in the study. Assessment of adverse events will include symptoms possibly related to the study medication and pregnancy expulsion, but will also include any additional adverse events experienced by the study participants.

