9.4.3 ANALYSIS OF THE SECONDARY OUTCOME VARIABLE(S)

- Resolution of EPL
 - Binomial outcome: Absence of gestational sac on transvaginal ultrasound examination on Day 3 follow up
 - o Binomial outcome: Need for additional dose of misoprostol within 30 days of treatment
 - Binomial outcome: Need for uterine aspiration within 30 days of treatment
- Side Effects/Adverse Events
 - Side Effects Binomial Outcomes (N, %)
 - Fatigue
 - Headache
 - Dizziness or lightheadedness
 - Chills
 - Nausea
 - Diarrhea
 - Vomiting
 - Severe cramping
 - Fever
 - Other
 - Adverse Events Binomial Outcomes (N, %)
 - Excess bleeding requiring blood transfusion
 - Pelvic infection requiring antibiotics
- Patient Acceptability
 - Likert Scale Ordinal Outcomes (Median, Counts)

- Would you use this combination of medications again if you had another early pregnancy loss?
- Would you recommend this combination of medications to a friend with early pregnancy loss?
- If it was possible to take the first medication at home (versus in clinic), would you be more or less likely to use this combination of medications again?
- If it were possible to take the first medication at a different time (versus during your appointment), would you be more or less likely to use this combination of medications again?

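### The Day 30 call asks specifically only about infection needing admission or IV antibiotics, but section 9.4.3 reports pelvic infection requiring antibiotics with no limit on route

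*Combined protocol and SAP*

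**What the plan says.** Section 8.3.4 defines what is asked at the Day 30 call: "Solicited information on adverse events will include increased bleeding requiring hospital admission or blood transfusion and infection requiring hospital admission or IV antibiotics". The next sentence reads: "All other adverse events will be identified based on unsolicited questioning during this telephone visit".

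Section 9.4.3 names two adverse-event outcomes: "Excess bleeding requiring blood transfusion" and "Pelvic infection requiring antibiotics". Section 9.4.4 refers back to these as the specific events of interest.

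Three other provisions bear on capture:

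- **General inquiry.** Section 8.3.4 also has the investigator ask about adverse events at each study visit. The Schedule of Activities (section 1.3) places an adverse-event review and a side-effects and adverse-events questionnaire at Visits 2, 3 and 4.
- **Chart.** Under section 8.3.5, an adverse event between visits "for which the participant seeks care at UNC Chapel Hill will be abstracted from the UNC EPIC electronic medical record".
- **Recording period.** Events are recorded "until 7 (for non-serious AEs) or 30 days (for SAEs) after the last day of study participation".

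**The concern.** An outcome that will be reported should be asked about in the terms in which it is reported. Here the solicited infection item is narrower than the outcome on severity of treatment. A woman who saw an outside clinician and took oral antibiotics for a pelvic infection can truthfully answer no to the solicited item and still have had the outcome event.

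The expected error runs one way, towards a lower reported infection rate. This is the first study of the drug for this indication (section 4.2), and a later trial would look to the pilot for its safety figures.

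**Working it through.** **1. Solicited items against reported outcomes**

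| | Solicited at the call (8.3.4) | Reported (9.4.3) | Is the reported event covered? |
|---|---|---|---|
| Bleeding | admission or transfusion | transfusion | Yes; the solicited item is the wider one |
| Infection | admission or IV antibiotics, any type of infection | pelvic infection, antibiotics, route not stated | No; outpatient oral treatment falls outside |

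The gap is confined to infection.

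**2. Routes by which an oral-antibiotic case could still be found**

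- Treated at UNC: the chart alert (8.3.4) and chart abstraction (8.3.5) should find it.
- Treated elsewhere: only the general inquiry or the Visit 4 questionnaire can find it. Neither is stated to ask about oral antibiotics. The questionnaire is not reproduced in the documents.

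**3. How much rests on the call**

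Under section 4.1, Visit 3 is attended only by women who still have a sac at Visit 2 and choose medical or expectant management. The others have no adverse-event review between Visit 2 and Visit 4, because the Schedule of Activities lists only liver tests for the Day 14 laboratory visit.

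- Visit 2: Day 3 ± 1, so Day 2 to 4.
- Visit 4: Day 30 ± 7, so Day 23 to 37.
- Interval without a scheduled inquiry: nominally 30 − 3 = 27 days; shortest 23 − 4 = 19 days; longest 37 − 2 = 35 days.

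For these women the call is the only scheduled adverse-event inquiry after about Day 3.

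**4. Effect of one missed event**

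The plan gives no infection rate and no power calculation, so there is no planned figure to reproduce. Exact (Clopper-Pearson) 95% intervals are used; with no events the upper limit is 1 − 0.025^(1/n).

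All enrolled, n = 40 (the sensitivity set in section 9.3):

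- One event reported: 1/40 = 2.5% (0.1 to 13.2%).
- That event missed: 0/40 = 0%, upper limit 1 − 0.025^(1/40) = 8.8%.

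Adherent women completing all visits (the main secondary set in section 9.3). Its size is unknown. As an illustration, suppose the section 9.1 targets are only just met at n = 40:

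- Adherence above 50%: at least 21 women. Retention above 90%: at least 37 women (36/40 is exactly 90%).
- With 21 adherent and 37 retained, the overlap lies between 21 + 37 − 40 = 18 and 21.
- One missed event is then 1/21 = 4.8 to 1/18 = 5.6 percentage points.
- With no events recorded, the upper limit is 1 − 0.025^(1/21) = 16.1% to 1 − 0.025^(1/18) = 18.5%.

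**The case against.** The strongest reply is that the plan does not rely on the solicited item alone. The investigator asks a general adverse-event question at each visit, the call is Visit 4, and a questionnaire is scheduled there. That stands. A reader might infer that an oral-antibiotic case is counted only if the woman volunteers it, and the documents do not support that. They support only that such a case is not stated to be asked about specifically. If the questionnaire already asks about any antibiotic, the only defect is that section 8.3.4 does not match it.

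Nor is the timing of the call the problem. The recording period runs past the last day of participation, so the gap lies in the question asked.

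A reader might also infer a larger fault in the 30-day treatment outcomes, "Need for additional dose of misoprostol within 30 days of treatment" and "Need for uterine aspiration within 30 days of treatment", because the call may fall anywhere from Day 23 to Day 37. Most of that does not hold:

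- **Second misoprostol dose.** Sections 4.1 and 6.1.2 tie it to Visit 2, or to Visit 3 if none was given before, so to dated visits around Days 2 to 9. That is well before the earliest call.
- **Treatment dates.** The Visit 4 form is not shown, so it cannot be said that dates are not collected.
- **Chart source.** Section 8.1 has care for the pregnancy loss documented in EPIC and in the study documentation, and section 10.1.9.1 refers to clinical data abstracted from EPIC. Chart abstraction is therefore not confined to adverse events.

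What remains is a late aspiration. Section 4.1 allows surgery at any of the weekly scans after Visit 3, and no rule states how an aspiration is dated against 30 days. The origin also varies: the call is set at study day 30 in section 4.1, 30 days after misoprostol in section 8.1, and 30 days after the study intervention in section 8.3.4. This is missing detail about what is probably a rare event.

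**Conclusion.** The mismatch between sections 8.3.4 and 9.4.3 on infection is plain on the text and should be corrected. Followed as written, the plan can under-count one of its two named adverse-event outcomes. The bleeding outcome is not affected.

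The size cannot be estimated. It depends on how often pelvic infection is treated orally outside UNC, and on how well the general inquiry and the unseen questionnaire find it. Per missed event, the effect is 2.5 percentage points in the all-enrolled set and about 5 points in a main secondary set of 18 to 21 women. That second figure assumes that the adherence and retention targets are only just met; a larger set would bring it closer to 2.5.

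The outcome is secondary and descriptive, and no hypothesis test depends on it. The point is minor.

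**What to change.** In section 8.3.4, and on the Visit 4 form if it does not already do so, solicit any pelvic infection treated with antibiotics, by any route and at any site of care. Record IV treatment or admission as a sub-item. Keep the existing adverse-event recording period. The cost is one reworded question.

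Optional tidy-up: state one origin for the 30 days, and count uterine aspirations by their recorded date from that origin, using the EPIC chart through Day 30 when the call is made earlier. This adds a short chart check for some women and changes nothing in their care.

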8.3.5 ADVERSE EVENT REPORTING

Adverse event reporting by patient self-report will take place at each study visit, both in person and via telephone. Additionally, any adverse event that happens between study visits for which the participant seeks care at UNC Chapel Hill will be abstracted from the UNC EPIC electronic medical record. All adverse events will be recorded on case report forms (CRF) and will be reviewed by the principal investigator and mentor. Case report forms should be documented within 24 hours of the event, and review of the case report forms will occur on a weekly basis.

Likely mild medication side effects as detailed for UPA include headache (18%), nausea (12%), abdominal pain (12%). Other infrequent mild side effects include dysmenorrhea, fatigue and dizziness [14]. All patients may experience pain and discomfort during the process of pregnancy expulsion; however, this pain and discomfort are not different than what a patient would experience not in the study. Assessment of adverse events will include symptoms possibly related to the study medication and pregnancy expulsion, but will also include any additional adverse events experienced by the study participants.

8.3.6 SERIOUS ADVERSE EVENT REPORTING

Based on prior studies of mifepristone and misoprostol, the rate of severe adverse event in this population is extremely low (approximately 1%). The study clinician will immediately report to the sponsor any serious adverse event, whether the adverse event is considered study intervention related, including those listed in the protocol and must include an assessment of whether there is a reasonable possibility that the study intervention caused the event. Study outcomes that are serious adverse events (e.g., all-cause mortality) must be reported in accordance with the protocol unless there is evidence suggesting a causal relationship between the study intervention and the event (e.g., death from anaphylaxis). In that case, the investigator must immediately report the event to the sponsor.

All serious adverse events (SAEs) will be followed until satisfactory resolution or until the site investigator deems the event to be chronic or the participant is stable. Other supporting documentation of the event may be requested by the study sponsor and should be provided as soon as possible.

Upon the first severe adverse event that occurs among study participants, the study will be stopped temporarily until review of the event by the UNC IRB. Following review of the severe adverse event, a decision will be made if the entire study will need to be stopped prematurely or if it is safe to continue the study.

The study sponsor will be responsible for notifying the Food and Drug Administration (FDA) of any unexpected fatal or life-threatening suspected adverse reaction as soon as possible, but in no case later than 7 calendar days after the sponsor's initial receipt of the information. In addition, the sponsor must notify FDA and all participating investigators in an Investigational New Drug (IND) safety report of potential serious risks, from clinical trials or any other source, as soon as possible, but in no case later than 15 calendar days after the sponsor identifies that the information qualifies for reporting.

Any serious liver injury case consistent with Hy's law will be reported as an expedited report to the FDA.

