5.4 SCREEN FAILURES

Screen failures are defined as participants who consent to participate in the study but are not administered the study intervention (ulipristal acetate) due to either participant withdrawal from the study or change in exclusion criteria following informed consent. A minimal set of information will be kept on all screen failure participants including eligibility screening checklist, informed consent documentation, demographic questionnaire (if completed), screen failure details and any severe adverse event (SAE). This information may be used in study reports, published materials, or to respond to regulatory authorities.

Additionally, a minimal set of information will be kept for patients screened for enrollment who do not meet eligibility criteria or who do not consent to participate in the study on the study screening register.

This information includes name, date of birth, referring physician, date of referral, date of contact with patient, and patient outcome (e.g. screen out, decline to participate, enroll in study). Following completion of enrollment of study participants, this information will be de-identified with just the number of patients in each outcome (screen out, decline to participate, enroll in study) for use in study reports, published materials, or to respond to regulatory authorities.

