8.3.2 DEFINITION OF SERIOUS ADVERSE EVENTS (SAE)

An adverse event (AE) or suspected adverse reaction is considered "serious" if, in the view of either the investigator or sponsor, it results in any of the following outcomes: death, a life-threatening adverse event, inpatient hospitalization or prolongation of existing hospitalization, a persistent or significant incapacity or substantial disruption of the ability to conduct normal life functions, or a congenital anomaly/birth defect. Important medical events that may not result in death, be life-threatening, or require hospitalization may be considered serious when, based upon appropriate medical judgment, they may jeopardize the participant and may require medical or surgical intervention to prevent one of the outcomes listed in this definition. Examples of such medical events include allergic bronchospasm requiring intensive treatment in an emergency room or at home, blood dyscrasias or convulsions that do not result in inpatient hospitalization, or the development of drug dependency or drug abuse.

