8.3.3 CLASSIFICATION OF AN ADVERSE EVENT

8.3.3.1 SEVERITY OF EVENT

For adverse events (AEs) not included in the protocol defined grading system, the following guidelines will be used to describe severity.

- Mild Events require minimal or no treatment and do not interfere with the participant's daily activities
- **Moderate** Events result in a low level of inconvenience or concern with the therapeutic measures. Moderate events may cause some interference with functioning.
- **Severe** Events interrupt a participant's usual daily activity and may require systemic drug therapy or other treatment. Severe events are usually potentially life-threatening or incapacitating. Of note, the term "severe" does not necessarily equate to "serious".

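### The automatic study pause in 8.3.6 is triggered by a severe event, an intensity grade, where the context shows a serious event was meant

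*Combined protocol and SAP*

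**What the plan says.** Section 8.3.6, headed as serious adverse event reporting, opens with an expected rate taken from earlier mifepristone and misoprostol studies: "the rate of severe adverse event in this population is extremely low (approximately 1" per cent). It then sets out how serious events are reported and followed up. The halt comes next: "Upon the first severe adverse event that occurs among study participants, the study will be stopped temporarily", pending review by the institution's IRB. The sentence after it keeps the same word: "Following review of the severe adverse event, a decision will be made if the entire study will need to be stopped prematurely".

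The two terms are defined in different places:

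- **Serious (8.3.2)** depends on outcome. The list begins "death, a life-threatening adverse event, inpatient hospitalization or prolongation of existing hospitalization" and goes on to incapacity, congenital anomaly and important medical events.
- **Severe (8.3.3.1)** is the top of a three-level intensity scale: events that interrupt usual daily activity and may need systemic drug or other treatment. The definition adds "Severe events are usually potentially life-threatening or incapacitating", and ends by noting that severe "does not necessarily equate to" serious.

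Section 5.4 lists, among the items kept for screen failures, "screen failure details and any severe adverse event (SAE"), although the abbreviation list in 10.3 expands SAE as Serious Adverse Event.

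**The concern.** A halting rule has to say exactly which event sets it off. This one uses a term that the protocol has already defined as something else, under a heading that names the other term. A coordinator who follows the text will look at the intensity grade; one who follows the heading will look at the outcome list. The two can disagree on the same event.

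This is the first study of ulipristal for this indication (4.2), and no other rule stops the study automatically on the occurrence of an event. The sponsor's review after the first 20 participants (8.2) is tied to enrolment count and liver tests. Suspension under 10.1.2 is discretionary. If the trigger is misread, either the study stops for an event that did not warrant it, or it continues without the IRB review that the rule was meant to guarantee.

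**Working it through.** **1. Which word was meant?** Three pieces of text point to *serious*: the heading of 8.3.6; the reporting and follow-up paragraphs around the rule, which concern serious events; and 5.4, which uses *severe* to spell out SAE, so the authors do interchange the words. Nothing in the protocol says the halt was deliberately tied to intensity, and 10.1.2 does not clarify it. The inference is strong but is not stated outright anywhere.

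**2. Can the literal rule be applied?** Yes. Section 8.3.4 requires the clinician's severity assessment for adverse events, and 9.4.4 plans to report other events as mild, moderate or severe. The grade that the literal rule needs will be on the case report form.

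**3. What does the literal rule do?** Crossing the two definitions gives four cases:

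| Event | Graded severe | Not graded severe |
|---|---|---|
| Serious (8.3.2) | Halt under either reading | Halt if *serious* is meant; no mandatory halt as written |
| Not serious | Halt as written; no halt if *serious* is meant | No halt under either reading |

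- *Halt for a non-serious event.* No expected or non-serious event is exempted. Section 8.3.5 says: "Assessment of adverse events will include symptoms possibly related to the study medication and pregnancy expulsion". Expulsion cramping could therefore qualify, but only if a clinician grades it severe under the definition in 8.3.3.1.
- *No halt for a serious event.* At the day-30 call, 8.3.4 asks specifically about bleeding or infection leading to hospital admission. Any such admission is serious under 8.3.2 whatever its intensity. If it is graded moderate, the mandatory halt does not follow.

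**4. How often would the halt occur?** Inputs: n = 40 (9.2) and p of about 0.01 (8.3.6). Assuming participants are independent, P(at least one) = 1 − (1 − p)^40.

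| p | Source | Expected participants, 40p | P(at least one halt) |
|---|---|---|---|
| 0.010 | 8.3.6 | 0.4 | 1 − 0.99^40 = 0.331 |
| 0.005 | assumed lower limit of *about 1%* | 0.2 | 1 − 0.995^40 = 0.182 |
| 0.015 | assumed upper limit of *about 1%* | 0.6 | 1 − 0.985^40 = 0.454 |

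The plan states no halt probability, so there is no figure to reproduce. The table shows that the rule has a realistic chance of being used. It does not measure the effect of the wrong word, because the protocol gives one rate and calls it severe. Purely as an illustration, severe-grade rates of 5%, 10% and 20% would give 87%, 98.5% and 99.99%. Those rates are assumptions with no support in the documents, and the conclusion does not rest on them.

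**The case against.** The best case on the other side has four parts.

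*Context settles the meaning.* If heading, neighbouring text and 5.4 all point to serious, staff will probably read it that way. That is likely, but a halting rule should not depend on readers overriding its words, particularly when the protocol has warned them that the two words differ.

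*Both failure cases are narrow.* Most hospital admissions would meet the severe description, and deaths and life-threatening events clearly would. To grade an admission moderate, a clinician must judge that it caused little inconvenience or concern and only some interference with functioning. On the other side, 9.4.3 lists severe cramping under side effects, apart from adverse events, and 8.3.5 treats expulsion pain as no different from what patients have outside the study. This narrows both cases. It closes neither, because 8.3.5 also brings expulsion symptoms into adverse event assessment and the severe definition is qualified by *usually*.

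*There are backstops.* Serious events go immediately to the sponsor (8.3.6). Unanticipated problems that are serious reach the IRB within 7 days (8.4.2). Case report forms are reviewed weekly (8.3.5), and an independent medical monitor reviews the study (10.1.6). Section 10.1.2 names grounds for suspension. All of this stands: a serious event would not go unaddressed. None of it is an automatic halt, and the 8.4.2 route requires the event to be unexpected, at least possibly related, and suggestive of greater risk.

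*Changing the word gives something up.* The literal rule errs towards caution by halting for severe non-serious events. That is true, and intent is inferred. If the sponsor does want intensity to trigger a halt, the rule should say so alongside serious events.

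**Conclusion.** The concern holds. As written, the mandatory halt is tied to an intensity grade, while the text around it shows that the outcome-based definition was intended. The literal trigger can be applied from data the study will collect, and it disagrees with the intended one in both directions. The consequence is limited to the automatic halt and its IRB review; reporting, monitoring and discretionary suspension are unaffected.

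The halt itself is a realistic prospect: 33% over 40 participants at the protocol's rate, or 18% to 45% under the assumed range of 0.5% to 1.5%. How far the wrong word moves that probability cannot be determined from the documents. The conclusion rests on the wording and on the inference about intent, not on these figures. It should be corrected; it does not undermine the feasibility analysis.

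**What to change.** In 8.3.6, replace *severe* with *serious (as defined in 8.3.2)* in three places and leave the rest of each sentence as it is:

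1. The sentence giving the rate of about 1%, after checking against the earlier studies that this is a serious-event rate.
2. The halting rule, so that its trigger is the first *serious adverse event (as defined in 8.3.2)*.
3. The follow-up sentence on the decision after review.

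In 5.4, write *serious adverse event (SAE)*, to agree with 10.3.

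The sponsor should confirm the intent when approving the change. The cost is four word substitutions in one IRB-approved amendment, with no change to visits, data collection or sample size. What is lost is the literal halt for severe but non-serious events, which the context indicates was not intended.
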